4.2. Selection of Study Population

Patients will be aged 6–17 years, with moderate to severe PANS with prominent and stable obsessive-compulsive disorder (OCD) symptoms. All patients will meet criteria for PANS, including the abrupt dramatic onset of OCD meeting DSM-5 diagnostic criteria for OCD as confirmed by the Mini International Neuropsychiatric Interview for Children and Adolescents (MINI-KID), and at least two of seven additional associated neuropsychiatric symptoms. Please refer to the protocol for a complete list of inclusion/exclusion criteria.

As a possible consequence of the adaptations mentioned in section 4.1 the selection criteria for the study population may be adapted based on the recommendations of the IDMC. In such a case the study protocol will be amended to reflect the different selection criteria.

4.3. Randomization, Stratification and Blinding

All patients qualified to participate in the study at Baseline (Week 0) will be randomized to one of two treatment sequences, (Panzyga – Placebo) or (Placebo – Panzyga), as detailed in section 4.1 above.

The randomization procedure will consider the following variables as stratification factors to balance the randomization also with respect to these patient characteristics of interest:

[REDACTED]	[REDACTED]	
[REDACTED]	[REDACTED]	[REDACTED]
[REDACTED]	[REDACTED]	[REDACTED]
[REDACTED]	[REDACTED]	[REDACTED]

Property of Octapharma. Do not copy or distribute without written permission.

5. Sequence of Planned Analyses

5.1. Interim Analysis

[REDACTED]

[REDACTED]

[REDACTED]

[REDACTED]

[REDACTED]

[REDACTED]

[REDACTED]

[REDACTED]	[REDACTED]

[REDACTED]

|| [REDACTED]

5.2. Final Analyses and Reporting

...open

... and write up

REDACTED

11. *What is the primary purpose of the following statement?*

...anyone can do it.

[REDACTED]	[REDACTED]	[REDACTED]
[REDACTED]	[REDACTED]	[REDACTED]
[REDACTED]	[REDACTED]	[REDACTED]

A large black rectangular redaction box covers the bottom portion of the page content, starting below the horizontal line and ending at the bottom edge of the page.

5.3. Control of type 1 error probability

Although neither changes of the endpoints nor the stated hypotheses are planned after the interim analysis the study will be using the combination pf p-values approach according to [Bauer & Köhne \[4\]](#) to maintain the overall type 1 error level.

[figure not shown]
In combination with the enrichment aspect of study this approach seems to better account for the potential differences in study cohorts between the two stages.

As recommended by [Liu & Chi \[3\]](#) an adjusted p-value will be calculated and presented in the final analysis in addition to the separate p-values p_1 and p_2 from the two study stages for better interpretability.

Property of Octapharma. Do not copy or distribute without written permission.

6. Sample Size Determination

The main endpoint of interest is the reduction of the total CY-BOCS score from Baseline to Week 9.

A document page with several large black redaction boxes. A faint watermark 'Proprietary - Not for distribution or reproduction' is visible across the page.

References

- [4] Bauer P, and Köhne K. Evaluations of experiments with adaptive interim analyses. *Biometrics* 1994; 50, 1029-1041.

6.1. Patient Replacement Policy

There will be no patient replacement in this study, but enrollment will continue until it is foreseeable that the number of patients required (according to the possible adaptations and the revised sample size determined at the interim analysis) for the evaluation of the primary endpoint will be achieved with the currently enrolled patients. 'Foreseeable' in this context means that the required number of evaluable patients will be achieved if the drop-out rate at the time remains unchanged for the remainder of the study.

6.2. Premature Termination of the Study

Both the Investigator and the Sponsor reserve the right to terminate the study at any time. In this event, any necessary procedure will be arranged on an individual study basis after review and consultation by both parties. In terminating the study, the Sponsor and the Investigator will ensure that adequate consideration is given to the protection of the patients' interests.

Regulatory authorities and IECs/IRBs should be informed in accordance with national regulations. Please refer to the protocol (sections 4.3.1 and 6.2.3) for further details on premature termination, in particular for the exact stopping criteria triggering temporary suspension/early termination of the entire study for an unacceptable increased venous TEE or acute renal failure risk in the Panzyga group compared to the placebo group.

In case the study is terminated prematurely, the SAP will be revised to address all issues arising from such special circumstances, and to confirm or redefine the scope of the analysis if necessary.

7. Analysis Populations

The following populations will be considered for the statistical analysis:

The **Intent-to-Treat set (ITT)** will include all randomized patients, regardless of whether the patient actually received study drug.

The **full analysis set (FAS)** will include all randomized patients who received at least part of one infusion of Panzyga or placebo

The **per-protocol set (PP)** consists of all patients of the FAS, excluding those with protocol deviations which may have an impact on the evaluation of the primary study outcome parameter(s). Only important protocol deviations with the potential to affect the study results substantially, or to invalidate the interpretation of the data obtained, will lead to exclusion of patients from the PP set; protocol deviations to be considered will include (but will not be limited to):

- Violations of the study entry criteria
- Withdrawal criteria that developed during the study
- Wrong treatment or incorrect dose
- Prohibited concomitant medication
- Incorrect completion of the CY-BOCS which affects the scoring

All protocol deviations documented during the conduct of the study or identified at the data review process prior to DB lock will be reviewed and classified as minor or major, and with respect to their importance for the planned analyses. This classification of protocol deviations is the joint responsibility of the clinical study manager, the study statistician, and Octapharma's responsible medical expert, and will be agreed and documented before the database is locked or unblinded.

For this study no separate safety population is defined as the FAS coincides with all patients who received at least part of one infusion of Panzyga or placebo. All safety data will thus be analyzed using the FAS. In the event that a patient takes the wrong study drug (i.e., did not take the randomized study drug), the actual treatment received will be used for safety analyses.

All efficacy analyses will primarily be based on the ITT population. In addition, analyses of the primary and secondary endpoints will be repeated on basis of the FAS, unless FAS and ITT coincide. All efficacy analyses will follow the intent-to-treat principle, i.e. patients will be analyzed according to the group they were originally assigned, regardless of what treatment they actually received.

Selected efficacy analyses, but at least the primary and secondary efficacy analyses, will be repeated for the PP population.

Screening failures will only be accounted for in the overall patient disposition, and individual data will be listed.

The assignment of each patient into the respective analysis populations will be determined before the statistical analysis in a data review meeting by a panel consisting of a medical expert from the sponsor, the clinical project manager, the data manager and the study statistician.

8. General Issues for Statistical Analysis

The primary target variable in this study is the CY-BOCS, the mean changes in the total CY-BOCS from Baseline to Week 9 will be compared between Panzyga and Placebo by a confirmatory statistical test to demonstrate superiority.

Descriptive summaries will be presented for each of the primary, secondary, and exploratory variables. In general, summaries will be presented by treatment group in a side-by-side fashion, using a set of standard summary statistics according to the different types of data:

Binary data (whether or not an event has occurred): counts and proportions

Count data (the frequency of an event in a set time period): rate (count per unit time)

Continuous data (measurements on a continuous scale, including quasi-continuous variables): arithmetic mean, standard deviation, median, minimum, maximum

Scales data (Ordinal and Non-ordinal): absolute and relative frequencies

Time-to-event data (how long it takes to observe the outcome of interest: time to event or last evaluation (censored data in case patients are lost to follow-up) and event rate). These parameters might not be tabulated separately, but can be included as an inset into a Kaplan-Meier plot of the product-limit survival function estimates.

Additional descriptive and exploratory statistics, such as geometric means, quartiles or confidence intervals, are included as appropriate. If not mentioned otherwise, confidence intervals are to be understood as two-sided, 95% confidence intervals.

Categorical data will generally be summarized with counts and percentages of patients. The denominator used for the percentage calculation will be clearly defined.

8.1. Analysis Software

Statistical analysis will be done with the statistical package SAS (version 9.4 or later).

8.2. Withdrawals

All patients enrolled in the trial will be accounted for, and withdrawals will be listed in full detail, including the reasons for withdrawal. Patients who withdraw from the study prematurely will be considered in all data presentations for which they contribute data in the ITT analysis populations.

All patients of the ITT will be included in the primary efficacy analysis, according to the intent-to-treat principle. Patients with missing data, including withdrawals, will be included in the analysis of the primary endpoint by means of the multiple imputation method assuming missing at random (MAR).

8.3. Handling of Missing Data

For the primary efficacy analysis, missing CY-BOCS results at Week 9 will be subjected to the multiple imputation method assuming missing at random, to include all randomized patients into the analysis.

In an additional sensitivity analysis such missing primary endpoint data will be replaced with the median change observed in the placebo group.

In case of missing weight measurements the last available body weight will be used for calculations related to dosing. In individual patient data listings missing data will however not be replaced by imputed values.

Missing data in secondary analysis variables will not be replaced by any method of imputation; instead, the frequency of missing values will be presented.

For adverse events the following will be applied:

AEs will be reported from the moment that informed consent has been given throughout the complete observation period; AEs with onset after start of the first IMP administration will be considered to be 'treatment-emergent' with respect to the treatment group of the patient at time of onset as defined in section 8.4 below.

If the start date and time of an AE are partially or completely missing, the AE will be considered as treatment-emergent in the analysis if it cannot be definitely shown that the AE did not occur or worsen after first IMP administration (worst case approach). Missing dates and times will not be replaced.

For medications the following will be applied:

A medication will be assumed to be concomitant if it cannot be definitely shown that the medication was not administered after the first IMP administration. Missing dates will not be replaced.

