**Number of Patients:**

It is estimated that a minimum of █ pediatric patients will need to be enrolled to ensure that █ patients are evaluable for the primary endpoint (considering a 10% dropout rate). The total number of patients enrolled for the final analysis may increase, depending on the outcome of the interim analysis.

Enrollment was staggered in the sense that it was paused after the first █ patients had been randomized and enrolled in the study, in order to enable a planned IDMC review of unblinded safety and PK data, including IgG trough levels. Enrollment resumed only after IDMC data review of the first █ patients had been completed, and the IDMC had recommended to continue enrollment in the study.

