**Figure 1: Scheme of Study Design**

### 3.3 Discussion of Study Design and Choice of Control Group(s)

#### 3.3.1 Study Design

Octapharma designed this prospective, multicenter, randomized double-blind superiority study comparing Panzyga with placebo (0.9% w/v sodium chloride) to confirm efficacy and safety of Panzyga in PANS patients. The study includes an additional double-blind, crossover safety and efficacy follow-up phase. In case of clinically important deterioration during the study, patients will be discontinued from the study, have termination visit procedures performed, and may optionally receive standard of care treatment at the site according to the treating physician.

Due to the previously described uncertainty on the expected effect size, the study will be set up in an adaptive, two-stage design using enrichment. This involves an interim analysis by an independent statistician after █ patients have completed the nine week treatment period (the entire study team will remain blinded until the end of the study).

In the context of this interim analysis, effect sizes for different subpopulations will be studied and statistically compared between treatments. After the interim analysis, the study may be adapted with respect to the study cohort and sample size. This may involve the exclusion of defined subgroups of patients for which no substantial treatment effect could be established.

Based on the observed effect sizes in the interim analysis, a re-estimation of the sample size for the post-interim analysis study part will be performed and the protocol may be amended accordingly. More details are provided in Section 9 of this protocol.

The study population will be prospectively balanced according to the choice of antibiotic prophylactic treatment, disease type (PANS/PANDAS) and treatment with stable dose of SSRIs.

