### 4.3.2 Premature Patient Withdrawal from Study Treatment

Patients may be withdrawn from study treatment for the following reasons:

- Occurrence of a condition or disease that interferes with the study treatment or represents an exclusion criterion.
- Administration of IVIG other than Panzyga. All patients who received at least one dose of the study treatment should be followed up per protocol until the study end without administration of the study product.

- Occurrence of an AE or SAE, which in the opinion of the investigator, precludes further treatment with study medication (Section 7.3.2).

If a patient shows worsening of their symptoms based on CGI-Improvement ratings, they will be presented to the site PI for review and treatment planning. Patients for whom worsening continues at a minimal level ("5" or "mildly worse") for an extended period of six weeks (2 visits) or moderately or greater level ("6" or "7"; much worse or very much worse) since last visit (up to three weeks) will be considered for premature withdrawal from the study drug and administration of appropriate standard of care treatment unless clinical interventions using approved study procedures and/or mediations have a reasonable likelihood to improve symptoms. Patients who experience an emergency worsening of symptoms may at the discretion of the site clinician be withdrawn from the study drug at any time to obtain necessary standard of care treatment. In addition, patients who develop exclusionary criteria (e.g. bipolar disorder, suicide attempt) will be withdrawn from the study drug and will receive appropriate standard of care treatment. All patients withdrawn from the study drug prematurely will be asked to continue the study as planned with modification of the study schedule (e.g. IMP administration and related to it safety lab tests will be omitted). Details of concomitant medications and procedures administrated per standard of care will be captured in patient case reports.

The eCRF will contain an End of Treatment and an End of Study page. The End of Treatment page will record whether the patient will be followed up per protocol, to allow for correct patient status tracking and to provide the reason for the drug withdrawal.

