Final 3.0	26-Jan-2021	[REDACTED]	Adjust wording to reflect revised eligibility criteria, unified use of term patient rather than subject, safety review of first 6 patients added, collection of non treatment-emergent AEs, introduction of the MINI-KID assessment, specific biomarker panel (autoimmune encephalopathy) replaced by backup blood sample for later analysis
Final 4.0	28-Jul-2021	[REDACTED]	Update based on Protocol Version 4.0: correct the number of items in SNAP-IV Scale; Correct the item score in CY-BOCS; Clarify the significance level for the interim analysis; Adjust wording in sample size estimation; Add covariates for multiple imputation.
Final 5.0	21-Jul-2023	[REDACTED]	Update based on Protocol Version 5.0 and 6.0: Add correlation analysis between CYBOCS and CGI-I. Add exploratory analysis for the percentage of patients with PANS improvement. Add interim review after 20 patients have completed blinded treatment.

Property of Octapharma. Do not copy or distribute without permission.

Abbreviations

ADHD	Attention-Deficit Hyperactivity Disorder	HTR	Hemolytic Transfusion Reaction
AE	Adverse Event	ICH	International Conference on Harmonization
ATC	Anatomical Therapeutic Chemical	IDMC	Independent Data Monitoring Committee
BMI	Body Mass Index	ITT	Intention-To-Treat
BW	Bodyweight	IVIG	Intravenous Immunoglobulin
CD	Conduct Disorder	MAR	Missing at Random
CGI	Clinical Global Impression	MedDRA	Medical Dictionary for Regulatory Activities
CGI-I	Clinical Global Impression - Improvement	MINI-KID	Mini International Neuropsychiatric Interview for Children and Adolescents
CGI-S	Clinical Global Impression – Severity	OC	Obsessive–Compulsive
CI	Confidence Interval	ODD	Oppositional Defiant Disorder
COIS	Parent & Child OC Impact Scale – Revised	PANDAS	Pediatric Autoimmune Neuropsychiatric Disorders Associated with Streptococcal infection
COIS-RC	Child Obsessive-compulsive Impact Scale - Revised – Child	PANS	Patients with Acute-onset Neuropsychiatric Syndrome
COIS-RP	Child Obsessive-compulsive Impact Scale - Revised – Parent	PP	Per Protocol
CSR	Clinical Study Report	PTQ	Parent Tic Questionnaire
C-SSRS	Columbia Suicide Severity Rating Scale	SAE	Serious Adverse Event
CY-BOCS	Children's Yale-Brown Obsessive Compulsive Scale	SAP	Statistical Analysis Plan
DB	Database	SNAP-IV	Swanson, Nolan, and Pelham Rating Scale
DSM	American Psychiatric Association's Diagnostic and Statistical Manual	SSRI	Selective Serotonin Reuptake Inhibitors

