4.1. Overall Study Design and Plan

Study NGAM-13 is designed as a prospective, multicenter, randomized, double-blind, parallel group, placebo-controlled, phase 3 superiority study, with an additional double-blind, crossover safety and efficacy follow-up phase.

In the first phase of the study, from enrolment to Week 9, patients will receive Panzyga or placebo administered 3 times within 9 weeks in 3-week intervals, according to their randomized treatment sequence. After Week 9 all patients will be switched to the alternative for another 3 treatments in the crossover phase of the study. Dosing and dosing intervals will be the same for all study drug administrations in both study phases, namely Panzyga 2 g/kg bodyweight (BW), administered as 1 g/kg BW daily for two consecutive days) or placebo (0.9% w/v sodium chloride infusion equivalent in volume to 1 g/kg BW Panzyga daily for two consecutive days).

Up to █ sites (USA and rest of the world) are projected to participate.

After the first █ patients have been enrolled, the study enrollment will be put on hold until the Independent Data Monitoring Committee (IDMC) has reviewed unblinded safety and PK data of these █ patients and given the green light to pursue the study.

The duration of the initial parallel-group phase will be 9 weeks, plus up to 28 days from screening to randomization, the duration of 2nd phase after the crossover will also be 9 weeks. After the initial phase patients will directly continue with the second phase without any wash-out time.

Patients eligible after screening will be randomized in a balanced 1:1 ratio to one of two treatment sequences:

- (Panzyga – Placebo): 3 administration cycles with Panzyga, followed by 3 administration cycles with placebo
- (Placebo – Panzyga): 3 administration cycles with placebo, followed by 3 administration cycles with Panzyga

The study population will be prospectively balanced according to the stratification factors specified in section 3.2.4 above. Psychological and behavioral evaluations, in particular the CY-BOCS, will be conducted at every visit, i.e. every 3 weeks during the initial parallel-group phase and at Week 18 / Final Visit; please refer to the protocol for the complete flow chart of assessments.

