2. Sample size re-estimation to achieve the desired power of 80% while maintaining the overall type 1 error rate of 2.5%. Please refer to section 6 for details on the sample size determination.

Study enrollment will continue while enough patient data is accrued to conduct the interim analysis. In case the sample size re-assessment does not result in a required total of more than the number of patients already enrolled at the time, enrollment will be stopped but patients already randomized will continue in the study until the planned end, i.e. for 18 weeks.

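### The one legible sensitivity analysis for missing Week 9 CY-BOCS never tests an outcome worse than the placebo median, and the protocol disagrees with itself on whether deteriorating patients stay in the study

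*SAP*

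**What the plan says.** **Missing data.** SAP 8.2 and 8.3 bring every randomized patient into the primary analysis by MI under MAR, withdrawals included. SAP 8.3 then adds: "In an additional sensitivity analysis such missing primary endpoint data will be replaced with the median change observed in the placebo group". The same value goes to both arms, whatever the reason for the gap. The repeats on the FAS and PP sets in SAP section 7 change the population, not the missing-data assumption. The SAP version log for Final 4.0 records "Add covariates for multiple imputation", so the imputation model has been worked on even though its text cannot be read.

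**Data available on a patient who leaves.** SAP 4.1 says the evaluations, "in particular the CY-BOCS, will be conducted at every visit, i.e. every 3 weeks during the initial parallel-group phase", and also at Week 18 or the final visit. Protocol 4.3.1 schedules an Early Termination Visit with the Week 18 procedures, so a CY-BOCS at exit is to be expected.

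**Planning figures.** The protocol outline sets enrollment "considering a 10% dropout rate". SAP 4.1 gives 80% power and an overall type 1 error of 2.5%.

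**Patients who deteriorate.** Protocol 3.3.1: "In case of clinically important deterioration during the study, patients will be discontinued from the study, have termination visit procedures performed". Protocol 4.3.2, repeated in the outline, has worsening patients considered for withdrawal from study drug, and then: "All patients withdrawn from the study drug prematurely will be asked to continue the study as planned with modification of the study schedule".

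**Not legible.** SAP 10.1 and 10.2, protocol 9.2.2 and 9.2.4, and the planned sample size and SD are blacked out.

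**The concern.** A sensitivity analysis should put pressure on the assumption behind the primary analysis, here MAR. Worsening is a named reason for stopping drug or leaving this trial. A child who worsens after the last rating is the case in which MAR can fail. The fill-in does not reach that case, because the lowest outcome it can assign is a typical placebo change. It also sets aside what is known about the patient: a child last rated as deteriorating at Week 6 is scored like the median placebo patient.

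Two things are at stake. A positive primary result could be called robust on the strength of a check that rarely disagrees with it. And the number of primary outcomes that depend on imputation at all turns on which of the two protocol rules a site follows for deterioration before Week 9.

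**Working it through.** The plan states no figure to reproduce here. Sample size and SD are blacked out, so every number below is an illustration, not an error rate of the trial's own two-stage test.

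**Step 1. How far the fill-in reaches.** Take the earlier IVIG trial in protocol 1.1 as an assumption: mean CY-BOCS decrease 24% on IVIG and 12% on placebo. Let m be the share missing and t the mean decrease in missing Panzyga patients. Put missing placebo patients at 12 and take the median as equal to the mean.

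Difference = (1 − m) × 24 + m × t − 12. At m = 0.10:
- MAR (t = 24): 12.0
- placebo-median fill (t = 12): 21.6 + 1.2 − 12 = 10.8
- no change (t = 0): 9.6
- 10% worse (t = −10): 8.6
- 25% worse (t = −25): 7.1

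The fill moves the estimate the right way, but it stops at 10.8.

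**Step 2. Error when the missing patients did worse than that.** Let the true all-randomized effect be zero. The fill-in is then biased by m × (12 − t). At m = 0.10 and t = 0, −10, −25 the bias is 1.2, 2.2 and 3.7 points. With 100 per arm (assumed), SD 29 and one-sided 2.5%, the fill-in rejects in 4.7%, 8.2% and 15.6% of 40,000 simulated trials. With equal random loss it stays near 2.5%, so single-value filling is not the fault in itself.

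**Step 3. MI and the fill-in side by side.** Assumed: 64 per arm; unit-variance changes at Weeks 3, 6 and 9 with adjacent-visit correlation 0.7; one-sided 2.5%; no true effect; no adaptation. MI uses arm and the Week 3 and Week 6 changes, 20 imputations and Rubin variance. At 64 per arm, 15%, 10% and 5% are 10, 6 and 3 patients. Ranges run from noisy to strict loss of the worst Week 9 scores. Agreement is the share of MI false positives that the fill-in also calls significant.

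| Missing, Panzyga/placebo | Exit depends on | MI error | Fill-in error | Agreement |
|---|---|---|---|---|
| 10%/10% | chance | 2.8% | 2.6% | – |
| 15%/5% | observed Week 6 score (MAR true) | 2.5% | 9.1% | – |
| 15%/5% | unobserved Week 9 score | 6.8% to 11.6% | 9.3% to 18.0% | 94% to 99% |
| 10%/10% | unobserved Week 9 score | 3.0% to 4.0% | 3.2% to 4.1% | 85% to 87% |
| 5%/15% | unobserved Week 9 score | 1.1% to 0.9% | 0.7% to 0.5% | 64% to 49% |

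The three Week 9 rows use 20,000 replicates each (Monte Carlo SE of the error rates 0.05 to 0.27 points); the first two use 10,000. Repeat simulations of the third row gave MI 6.5% to 11.9% and 7.1% to 12.4%.

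**Step 4. Hand check of the second row.** The worst 10 of 64 on Week 6 average 1.53 SD, hence 0.7 × 1.53 = 1.07 SD at Week 9. The worst 3 of 64 average 2.09 SD, hence 1.46 SD. Filling both with a value near zero flatters Panzyga by (10/64) × 1.07 − (3/64) × 1.46 = 0.167 − 0.068 = 0.10 SD. With SE √(2/64) = 0.177 that is 0.56 SE, and 1 − Φ(1.96 − 0.56) is about 8%. Filling also shrinks the SE a little, which accounts for the simulated 9%.

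**Step 5. What a delta adjustment adds.** Of the MI false positives at 15%/5% with Week 9-driven loss, 36% to 40% survive a delta of 0.5 SD added to imputed Panzyga values; at 10%/10% about 50% survive. The median delta that overturns the result is 0.4 SD for the former and 0.5 to 0.6 SD for the latter. With a true 0.5 SD effect and random loss it is 1.2 SD at 15%/5% and 1.9 SD at 10%/10%, so the tipping point separates the situations. In those true-effect cases the fill-in keeps 90% and 95% of significant MI results, and delta 0.5 SD keeps 80% and 89%.

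**Step 6. Other inputs.** If 2.5% is two-sided (1.25% per side), the third row becomes MI 3.9% to 7.4%, fill-in 5.4% to 11.9%, agreement 93% to 98%. With 40 or 100 per arm and correlation 0.5 or 0.85, agreement is 82% to 100% at 15%/5% and 82% to 93% at 10%/10%.

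**Step 7. The two protocol rules.** Section 3.3.1 takes the deteriorating patient out of the study. Section 4.3.2 takes the patient off drug and asks for continued attendance. Section 3.3.1 does not define its threshold, so it might be meant for a different group. But 4.3.2 already covers emergency worsening and the two worst CGI-I grades, so no separate group is evident. For deterioration before Week 9, one reading gives an observed Week 9 score; the other gives an early-termination score and an imputed Week 9.

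**The case against.** The strongest reply concerns mechanism. Withdrawal for worsening is mainly triggered by CGI-I ratings at study visits, and CY-BOCS is taken every three weeks, so much of the loss would depend on observed data. MI is then valid, as the second row of the table shows. This stands, and it rules out an inference that a reader might draw: that the primary analysis runs at 7% to 12% error. That needs loss driven by unseen scores, such as emergency worsening between visits, and concentrated on Panzyga. The documents do not predict that; protocol 1.3 even lists worsening as a risk of placebo assignment. The same row, however, counts against the fill-in, which is then the less valid of the two analyses.

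Second, a placebo-based fill is a recognised stress test. That stands too. A reader might infer that the plan tests nothing less favourable than MAR; that is wrong if the drug works. The limit is the placebo median.

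Third, the blacked-out sections may hold further sensitivity analyses. Their absence cannot be claimed, and neither can a missing imputation model. The request is therefore conditional.

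Fourth, the Early Termination Visit should yield an exit CY-BOCS, which softens the contrast between measured and imputed. Whether the MI uses it is not legible, and the simulated MI had no such score.

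**Conclusion.** The point holds in limited form and should be addressed. The only legible missing-data check on the primary endpoint cannot test outcomes worse than the placebo median, and it discards the patient's own scores. It can therefore mislead in two ways under greater loss on Panzyga: raising a false signal when MAR is true (about 9% against 2.5%), or endorsing an MI false positive when MAR fails (over 90% agreement). Under equal loss the MI excess is small, and under greater placebo loss both analyses are conservative. The documents do not say which arm would lose more. The sizes rest on an assumed sample size, correlation, missingness split and one-sided level, without the combination test. Confidence is medium.

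The conflict between protocol 3.3.1 and 4.3.2 does not depend on any of these assumptions.

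**What to change.** 1. Unless SAP 10.1–10.2 or protocol 9.2.2/9.2.4 already contain it, replace or supplement the single-value fill in SAP 8.3 with a delta-adjusted tipping-point analysis built on the MI. Vary delta separately by arm, use Rubin variance, and report the smallest delta that changes the conclusion with a judgement of its plausibility. Use the early-termination CY-BOCS in the imputation model if it is not already there.
2. Reconcile protocol 3.3.1 with 4.3.2 and the outline, and state for which patients the Week 9 CY-BOCS is to be collected. Which clinical rule is right is not for this review to say.

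The cost is one SAP paragraph, modest programming and a protocol clarification, all settled before unblinding. The downside is a sensitivity result that may look less favourable: with a true 0.5 SD effect, delta 0.5 SD on Panzyga alone loses about 11% to 20% of significant results. A large enough delta overturns any finding, so the plausible range should be fixed in advance.
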